4.2. Study Dosing Regimens

4.2.1. Treatments Administered

Patients enrolled to Arm 1 may receive up to four 21-day cycles of SYNB1891 monotherapy. On Days 1, 8, and 15 of Cycle 1 and Day 1 of Cycles 2 through 4, patients will receive an i.t. injection of SYNB1891 into an eligible lesion. If the initial eligible lesion undergoes complete regression and is no longer injectable (at the discretion of the Investigator), a subsequent eligible lesion (until no more eligible lesions remain) may be injected.

At the end of Cycle 4, patients in Arm 1 who do not have progressive disease (i.e., those who achieve and sustain complete response [CR], partial response [PR], or stable disease [SD]) may receive additional cycles of SYNB1891 administered by i.t. injection on Day 1 of each cycle for up to 24 months (i.e., Cycles 5 to 35) after the initial dose of study treatment until documentation of progressive disease or other discontinuation criteria, satisfaction of a predefined study stopping rule, or no eligible lesions remain.

Patients enrolled to Arm 2 may receive up to four 21-day cycles with SYNB1891 administered by i.t. injection into an eligible lesion on Days 1, 8, and 15 of Cycle 1 and Day 1 of Cycles 2 through 4. In addition, atezolizumab will be administered in accordance with its recommended dose and schedule (1200 mg IV Q3W) on Day 1 of each of the 4 planned cycles. On days when atezolizumab and SYNB1891 are both administered, SYNB1891 will be administered first, followed by at least 1 hour of observation prior to the atezolizumab infusion. Patients in Arm 2 who do not have progressive disease (i.e., those who achieve and sustain CR, PR, or SD) at the end of Cycle 4 on combination therapy may receive additional cycles of SYNB1891 and atezolizumab for up to 24 months (i.e., Cycles 5 to 35) after the initial dose of study treatment until documentation of progressive disease or other discontinuation criteria, satisfaction of a predefined study stopping rule, or no eligible lesions remain.

Locating and/or injecting the lesion may be performed using guided imaging at the discretion of the Investigator.

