7.3. Efficacy Assessments

Disease response status will be assessed in the SYNB1891-injected lesion(s), and an overall analysis of potential responses in up to 5 noninjected target lesions will be performed using appropriate imaging at screening and every 2 cycles on study (i.e., at the end of every even-numbered cycle) for the duration of the treatment period and at the EOT visit (unless imaging has been performed within 8 weeks prior to the EOT visit). Every effort should be made to assess each lesion that is measured at screening using the same imaging method(s) throughout the study to enable a consistent comparison. Injected lesions that are reduced in size on study to the extent that they are no longer able to sustain injections will continue to be monitored for response.

Tumor response will be evaluated by the local Investigator using appropriate imaging in accordance with RECIST 1.1 ([Eisenhauer et al 2009](#) and [Appendix 1](#)), iRECIST ([Seymour et al 2017](#) and [Appendix 2](#)), and/or LYRIC ([Cheson et al 2016](#) and [Appendix 3](#)).

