7.5.2. Safety Follow-up Visit

All patients will attend a Safety Follow-up visit 30 ± 5 days after the last dose of study treatment.

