- If the repeated assessment confirmed as no disease progression and later SD, PR or CR occur, the initial diagnosis of PD will not be considered as the endpoint. Patients will continue further assessments until consecutive disease progression assessments occur.
- If the repeated assessment confirmed no disease progression and no later SD, PR or CR occur, and patients stop treatment due to not clinically stable or the patients die from their cancer, then the first unconfirmed progression should still be used as the endpoint (Seymour et al 2017).
- If the patients do not do a repeat assessment due to any other reasons, the unconfirmed PD date will be used as the endpoint.

For patients with lymphoma and evaluated by LYRIC, if they are categorized as having any of the IR response, repeat imaging should be obtained after an additional 12 weeks.

- If a patient is assessed as having IR and then “true” progressive disease at a subsequent time point, the IR assessment should subsequently be corrected to progressive disease and the date will be used as the PD endpoint for the relevant time to event analysis,
- If repeated imaging could not be obtained, the IR category will still be used as the endpoint.
- **Time to Progression (TTP):** defined as the time from the first SYNB1891 injection (Day 1) to PD. Patients who complete the study without PD or death will be censored at the day of their last visit. Patients

who discontinue or die due to disease progression, the endpoint will be the last assessment date prior to discontinue or death. Patients who discontinue or die not due to disease progression will be censored at their last tumor assessment.

- **Progression Free Survival (PFS):** defined as the time from the first SYNB1891 injection (Day 1) to PD or death, whichever is first, from any cause. Patients who complete or discontinue the study without disease progression or death will be censored at the last Response assessment date.

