- **Duration of Response:** defined as the time from the first day the patient achieves objective response (PR or CR) to the day the patient's response falls to PD. Patients who do not achieve an objective response of a PR or CR during the study are excluded from this analysis. Patients who achieve objective response and remain the response at the end of the study will be censored at their last tumor assessment visit. If patients discontinued study due to disease progression after achieving objective response, they will not be censored, and disease progression date will be the endpoint. If patients discontinued study not due to disease progression after achieving objective response, they will be censored at their last tumor response assessment date.

Waterfall plots for tumor response by individual will be presented. The plots will have one bar per subject sorted from worst to best response with color by dose administered. Tumor response will be calculated based on the type of cancer that the patient has with the appropriate measure using either RECIST or LYRIC; an indicator will be placed on the figure to show if the response for each subject is from “R”, RECIST, or “L”, LYRIC. One waterfall plot will indicate best tumor response (minimum percent change from baseline) at any time point for each subject. One waterfall plot will represent injected and non-injected tumors.

Spaghetti plots for tumor response by time will be presented. One line will be drawn per subject with color by response type (see Section VII.2). The horizontal axis will be time and the vertical axis will be percent change from baseline in tumor response. One spaghetti plot will be generated for all patients at all times. One set of spaghetti plots will be generated with one panel per analysis type (RECIST/ iRECIST, or LYRIC) and only patients who apply for the current analysis type will be shown.

Swimmer plots will be generated with panels by analysis type (RECIST/iRECIST, or LYRIC). The plots will have one horizontal bar per subject firstly sorted by best response type (see Section VII.2), and then sorted by from best to worst time to start that response; when best to worst time to start that response does not apply (e.g. NE for RECIST), patients will be sorted by

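### TTP censors study completers at their last visit, PFS at their last tumor assessment, so TTP counts time in which progression was not assessed

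*SAP*

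**What the plan says.** SAP Section VII.A.3 measures TTP from the first SYNB1891 injection to progressive disease (PD). Its censoring rules, with those of the neighbouring endpoints, are:

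- TTP, completers with no event: "Patients who complete the study without PD or death will be censored at the day of their last visit".
- TTP, patients who leave or die for other reasons: "Patients who discontinue or die not due to disease progression will be censored at their last tumor assessment".
- PFS: "Patients who complete or discontinue the study without disease progression or death will be censored at the last Response assessment date".
- Duration of response: responders still in response at study end "will be censored at their last tumor assessment visit".

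On visits, Protocol Section 7.5.2 states: "All patients will attend a Safety Follow-up visit 30 ± 5 days after the last dose of study treatment". Under Protocol Section 7.3, imaging is done at screening, "at the end of every even-numbered cycle", and at the end-of-treatment (EOT) visit "unless imaging has been performed within 8 weeks prior to the EOT visit". The event schedules (Protocol Tables 19 and 20, SAP Appendix 3) mark tumor imaging at EOT but not at Safety Follow-up.

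The SAP summarizes these endpoints by Kaplan-Meier medians and quartiles for each arm and cohort. TTP and PFS tables are both planned, by RECIST 1.1 and by LYRIC (Appendix 5, Tables 15 to 18). SAP Section II lists both endpoints as exploratory.

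**The concern.** Progression status is known only up to the last tumor assessment. SAP Section V.F takes the progression date from the scan that established it, so the days between the last scan and a later visit without imaging cannot ordinarily yield a TTP event. The TTP rule still counts them as event-free.

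Two inconsistencies follow. For a completer with neither progression nor death, TTP and PFS rest on the same scans and should be censored on the same day, but the SAP gives TTP the later date. Within TTP, a completer is followed to the last visit and a patient who leaves for another reason only to the last scan. The SAP gives no reason for either difference. At stake are the risk sets, and possibly the reported median or quartiles, in cohorts that may hold as few as 3 patients.

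**Working it through.** The plan states no figure to reproduce, so the check is date arithmetic on the schedule.

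**Inputs**
- Cycle length 21 days (Protocol 4.2.1).
- Scans at the end of even-numbered cycles (Protocol 7.3; SAP VII.A.1).
- EOT visit 0 to 14 days after the last dose (Protocol 7.5.1).
- EOT scan waived if one was done in the previous 8 weeks, that is 56 days (Protocol 7.3).
- Safety Follow-up 25 to 35 days after the last dose (Protocol 7.5.2).

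**Formulas**
- Cycle k Day 1 = 1 + 21(k − 1); end of Cycle k = 21k.
- Unassessed time credited = Safety Follow-up day − last scan day.

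**Dates**
- End of Cycle 2 = Day 42. Cycle 4 Day 1 = 1 + 63 = Day 64. End of Cycle 4 = Day 84.
- End of Cycle 34 = Day 714. Cycle 35 Day 1 = 1 + 714 = Day 715.

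| Completer | Last scan | Safety Follow-up | Gap (days) |
|---|---|---|---|
| Last dose Cycle 35 Day 1 | Day 714 | 715 + 25 to 35 = Day 740–750 | 26–36 |
| Last dose Cycle 4 Day 1, end-of-Cycle-4 scan done | Day 84 | 64 + 25 to 35 = Day 89–99 | 5–15 |
| Last dose Cycle 4 Day 1, no scan after Cycle 2 | Day 42 | Day 89–99 | 47–57 |

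In the first row the latest EOT visit is 715 + 14 = Day 729, 15 days after the scan, so the waiver applies. In the third row it is 64 + 14 = Day 78, which is 36 days after the Day 42 scan. That is inside the waiver, and it also falls before the end-of-Cycle-4 scan is due.

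SAP Section IV.B places the scan at the start of odd-numbered cycles instead, which moves each scan one day later and shortens each gap by one day.

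**Limits of the rule.** If a scan is done at EOT, the gap runs from 25 − 14 = 11 to 35 − 0 = 35 days. If the waiver is used to its limit, with a scan exactly 56 days before EOT, it runs from 11 + 56 = 67 to 35 + 56 = 91 days. The gap is above zero in every case.

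**Effect on a Kaplan-Meier estimate (assumed data).** Take 10 patients: PD on Days 42, 42, 84, 84, 126 and 126, and four completers whose last dose is Day 64 and last visit Day 94. After Day 42, S = 8/10 = 0.80.

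| Completers censored at | At risk Day 84 | S(84) | Median |
|---|---|---|---|
| Day 42 (last scan; no end-of-Cycle-4 scan) | 4 | 0.80 × 2/4 = 0.40 | 84 days |
| Day 94 (last visit) | 8 | 0.80 × 6/8 = 0.60 | 126 days |
| Day 84 (end-of-Cycle-4 scan done) | 8 | 0.60 | 126 days |

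If the four instead complete at about 24 months, censoring at Day 715 or Day 745 gives the same curve: S(126) = 0.60 × 4/6 = 0.40, median 126 days.

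**The case against.** The strongest reply is that the estimates will seldom move. Scheduled scans fall on a 42-day grid, and a later censoring date matters only if another patient's PD date lies inside the gap. For the four-cycle completer scanned on Day 84, the gap ends by Day 99 and the next grid date is Day 126. For the 35-cycle completer it ends by Day 750 and the next would be Day 756. This stands for patients scanned exactly on schedule. It does not remove the problem, because EOT scans, permitted delays and visit windows take PD dates off the grid, and the Day 42 gap spans the Day 84 scan.

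The 47 to 57 day case, and with it the shift in the median from 84 to 126 days, needs a patient who has no end-of-Cycle-4 scan, has the EOT scan waived and still counts as completing the study. The SAP does not define completion for this rule. If such a patient is classed as discontinued, the next TTP sentence already censors at the last tumor assessment. This also stands, so that case is conditional. With the Day 84 scan in place, the worked example shows no difference.

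The last visit is also undefined, and the phrase may be a drafting slip. Safety Follow-up is nevertheless the natural reading of the schedule, and no text equates the last visit with the last assessment.

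Finally, TTP is exploratory, has no hypothesis test and feeds no dosing decision. That limits the weight of the point but does not answer it.

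**Conclusion.** The concern holds. The TTP rule for completers conflicts with the PFS rule, the duration-of-response rule and the rest of the TTP rule, and it counts unassessed days as progression-free. The excess per completer is 26 to 36 days after 35 cycles, 5 to 15 days after four cycles with the Day 84 scan, and 47 to 57 days under the conditional case above.

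These figures assume dosing on schedule and Safety Follow-up as the last visit. The number of patients affected cannot be derived from the documents but is probably small. The effect on reported medians and quartiles is likely to be nil or slight, and could be material only in a small cohort with early completers and a missed or waived scan. This is a minor correction.

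**What to change.** In the TTP definition in SAP Section VII.A.3, replace the day of the last visit with the date of the last tumor response assessment as the censoring date for patients who complete without PD or death. The unassessed interval then becomes zero, and TTP agrees with PFS, with duration of response and with its own rule for other discontinuations.

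The cost is one phrase in the SAP. Censored TTP values become slightly shorter. No new data, protocol amendment or change to any clinical procedure is needed.

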Importantly, if a patient is assessed as having IR and then “true” progressive disease at a subsequent time point (without an intervening objective response between IR and progressive disease), the IR assessment should subsequently be corrected to progressive disease for reporting purposes to the date of the prior designation of IR. While these lesions may remain stable during the time of observation, the initial designation of IR should be changed to progressive disease.

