Patients’ best overall response will be selected based on the overall response order (CR, PR, SD, PD, NE for RECIST; CR, PR, SD, PD, IR1, IR2, IR3 for LYRIC) through the study. Objective Response Rate (ORR), defined as the proportion of patients’ overall response achieving a PR or CR at any time on the study, will be summarized descriptively by arm and cohort. In addition, an exact 90% confidence interval (CI) will be presented for RP2D cohort in Arm 2. Note that the definition of the Efficacy Population includes all treated patients who have an on-treatment response assessment or who discontinued study early due to disease progression; therefore, all Efficacy Population patients will be included in the denominators for percentage even if the patient had a Not Evaluable response. The best overall response and objective response rate will be summarized separately for each assessment method (RECIST, iRECIST, or LYRIC).

Similarly, the proportion of patients with a PR and the proportion of patients with a CR at any time during the study will be summarized as part of the best

overall response. The sum of diameters and change from baseline will also be summarized, by arm and cohort at each assessment visit.

All overall tumor and lymphoma response data will be presented in patient listings.

3. Determination of Time to Event Endpoints

Below is a list of events definitions for the solid tumor patients with a confirmed response according to RECIST v1.1 and iRECIST, and lymphoma patients with response according to LYRIC. The number of events and the number of censored patients will be summarized. The median time to event (reported in days) and the 25th and 75th percentiles on the time to event for each arm and cohort will be summarized using Kaplan-Meier estimates. Progression-Free Survival graphs will also be provided.

When calculating the endpoint that involve PD diagnosis date, such as time to progression or progression free survival, below rules will apply to account for the repeated PD response assessment per iRECIST:

- When a patient has disease progression per RECIST, if the repeated assessment confirmed as disease progression according to iRECIST criteria, the first PD date will be used in the endpoint calculation.

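### The SAP dates the TTP event of patients who stop or die from progression at their last assessment, whether or not it showed PD, so TTP can precede PFS and conflict with the SAP's first-PD-date rules

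*SAP*

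**What the plan says.** SAP VII.A.3 defines TTP as the time from the first SYNB1891 injection to PD. It then gives three rules.

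- Completers: "Patients who complete the study without PD or death will be censored at the day of their last visit".
- Stopping or death from progression: the rule is for those "who discontinue or die due to disease progression, the endpoint will be the last assessment date prior to discontinue or death".
- Stopping or death for another reason: these patients "will be censored at their last tumor assessment".

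PFS is "defined as the time from the first SYNB1891 injection (Day 1) to PD or death, whichever is first, from any cause"; patients with neither event "will be censored at the last Response assessment date". Duration of response (DOR) ends at the progression date when a responder leaves the study for progression, and is otherwise censored at the last tumour assessment.

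The same section has PD-date rules that it applies expressly to TTP and PFS. When repeat assessment confirms PD, "the first PD date will be used in the endpoint calculation". When PD is unconfirmed and the patient stops as clinically unstable, or "the patients die from their cancer, then the first unconfirmed progression should still be used as the endpoint". For lymphoma, an immune response (IR) followed by true PD is corrected to PD and that date is used. Protocol Appendix 3 makes the date explicit: "the IR assessment should subsequently be corrected to progressive disease for reporting purposes to the date of the prior designation of IR".

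SAP V.F (Outcome Dates) says that a progression date normally comes from the scan used to determine progression, and that outcome dates are not otherwise imputed.

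**The concern.** The TTP sentence has no condition that the last assessment showed PD, or that it was the first to do so. Two faults follow, in opposite directions.

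Without a PD scan, progression is recorded on a date when the scan showed none. The same scan would be a censoring date had the patient stopped for another reason. PFS counts every PD and every death, so a TTP event before the PFS event is incoherent. A responder shows it plainly: with a partial response on the last scan and then a stop for clinical progression, the TTP event falls on the scan that established the response, while DOR runs on to the progression date.

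With a PD scan followed by another scan, the sentence picks the later one, against the first-PD-date rules.

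TTP is a protocol exploratory objective. SAP Appendix 5 plans TTP and PFS tables (Tables 15 to 18), also for the interim at the end of Arm 1, and VII.A.3 asks for Kaplan-Meier medians and quartiles by arm and cohort. Cohorts start at 3 patients. With three events the median is the second-smallest time, so one misdated event can move it.

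**Working it through.** The plan gives no TTP or PFS figure to reproduce, so the check applies its rules to hypothetical patients.

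**Inputs from the documents**
- Cycles last 21 days and imaging is done at the end of even-numbered cycles (protocol 4.2.1 and 7.3): Days 42, 84, 126.
- The end-of-treatment (EOT) visit is within 14 days of the last dose. Its scan is waived if imaging was done in the previous 8 weeks (protocol 7.5.1 and 7.3).
- Safety follow-up is 30 ± 5 days after the last dose (protocol 7.5.2).
- Time = event date minus reference date (SAP V.F), that is, day − 1. The SAP's duration convention would add 1 day to every value and leave the gaps unchanged.

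The patient timelines are assumptions.

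| Patient | TTP sentence | PFS or PD-date rules | Difference |
|---|---|---|---|
| A. Stable disease (SD) Day 42, no PD scan, cancer death Day 83 | 42 − 1 = 41 | PFS 83 − 1 = 82 | 41 days early |
| B. SD Day 42, last dose Day 64, EOT scan waived, cancer death Day 95 | 41 | PFS 95 − 1 = 94 | 53 days early |
| C. PD Day 42, confirmed Day 84, then stops | 84 − 1 = 83 | First PD 42 − 1 = 41 | 42 days late |
| D. Lymphoma: IR Day 42, true PD 12 weeks later, then stops | 42 + 84 = 126; 126 − 1 = 125 | IR date 41 | 84 days late |
| E. PD Day 42, no repeat scan, stops Day 45 | 41 | 41 | none |

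**Can patient B occur?** Cycle 4 Day 1 is 1 + 3 × 21 = Day 64. The latest EOT visit is Day 64 + 14 = Day 78, which is 78 − 42 = 36 days after the scan. That is inside 56 days, so no EOT scan is required. Safety follow-up falls on Days 89 to 99, and the death on Day 95 lies within that window.

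**Discontinuation without a PD scan, patient alive.** Take SD on Day 42 and a stop for clinical progression on Day 60. The TTP sentence gives an event at 41 days. The PFS text gives no PD date; if only scan-documented PD counts, PFS is censored at 41 days. If TTP alone were moved to Day 60, it would be an event at 59 days against PFS censored at 41. The rule therefore has to cover all the endpoints.

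**Screening scan only (conditional).** The Efficacy Population includes patients who stopped for progression before any response assessment. If *assessment* means tumour assessment, the only date available is the screening scan, 0 to 28 days before Day 1, so TTP is 0 to −28 days. Example: scan 14 days before Day 1, cancer death Day 35, giving TTP −14 and PFS 34. After a last dose on Cycle 1 Day 15, the latest EOT visit is Day 29, at most 28 + 28 = 56 days after the screening scan, so the EOT scan can be waived. After a Cycle 2 Day 1 dose (Day 22) the latest EOT visit is Day 36, which is 36 to 63 days after a scan done 1 to 28 days before Day 1, so it is not always waived.

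**The case against.** The strongest reply is that the sentence is a fallback for patients without a PD scan. TTP is defined as time to PD, the PD-date rules name TTP, the SAP has its own LYRIC rule just above the TTP definition, and V.F ties progression to the scan that determined it. For patients C and D this carries weight: a reader might infer that the programmer has no guidance, but these texts favour the first PD date. What remains is that the sentence is not limited to patients without a PD scan, and nothing says which rule prevails. The reply does not help patients A and B, because there the fallback itself produces the wrong date.

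On the screening-scan case, a reader might infer that negative times are certain. They are not. The SAP does not define *assessment*, although its next sentence speaks of tumour assessments; if any visit counts, the case disappears. Protocol Appendix 1 also allows extra scans on suspicion of progression. The sentence introducing the definitions mentions only patients with a response, which read literally would exclude these patients, although Appendix 5 assigns the TTP tables to the Efficacy Population.

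A reader might also want a frequency. The documents give neither the share of progressions without a PD scan nor a distribution of progression times, so any rate would rest on invented inputs. Finally, TTP is exploratory and descriptive. That stands, and it limits the importance of the point.

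**Conclusion.** The point holds. Followed as written, the sentence gives a wrong event date when a patient dies of progression without a PD scan and the last assessment precedes death. The examples are 41 and 53 days early. From the 42-day scan interval a reader might infer that 41 days is the limit; patient B shows that it is not. When a later scan follows the first PD, the literal reading is late by 42 days in the solid-tumour example and 84 days in the lymphoma example, but these are conflicts between rules that the rest of the SAP helps to resolve. Zero or negative times are possible only on one reading of an undefined word. When the last assessment is the first PD scan, there is no error.

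The sizes rest on the nominal schedule and the assumed timelines. Dose-limiting toxicity, the MTD and the RP2D are untouched. The sentence should be corrected before the TTP and PFS tables are programmed.

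**What to change.** Replace the TTP sentence in SAP VII.A.3.

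1. **PD scan exists:** the event date is the first PD date under the section's existing rules, including the LYRIC rule (an IR later corrected to PD counts as PD). Never date progression at an assessment that did not show it.
2. **No PD scan:** state one rule for TTP, PFS and DOR alike. Death from progression is an event at the death date. Discontinuation for clinical progression is either an event at the recorded progression or discontinuation date, with a footnote, or censored at the last evaluable tumour assessment; report the other option as a sensitivity line. Either is defensible: protocol Appendix 1 treats symptomatic deterioration as a reason to stop, not as an objective response. State the order when a patient stops for clinical progression and later dies.
3. **Completers:** censor TTP at the last evaluable tumour assessment, in line with PFS and DOR, or at Day 1 if there is none after the first dose.

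The cost is a few sentences of SAP text, a table footnote and minor programming. Progression deaths without a PD scan move later, to the death date; events dated at a repeat scan move back to the first PD.
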